### 7.3 Relationship of AEs to Study Medication

The investigator will document her/his opinion of the relationship of the AE to treatment with study medication using the criteria outlined in Table 5. An AE for which there is a 'reasonable possibility' that the study medication caused the AE is otherwise referred to as suspected adverse reaction (SAR). 'Reasonable possibility' means there is evidence to suggest a causal relationship between the study medication and the AE.

**Table 3 Relationship of AEs to Study Medication**

Relationship	Description
Definite	A reaction that follows a reasonable temporal sequence from administration of the drug or in which the study medication level has been established in body fluids or tissue; that follows a known or expected response pattern to the suspected drug; and that is confirmed by improvement on stopping or reducing the dosage of the study medication, and reappearance of the reaction on repeated exposure.
Probable	A reaction that follows a reasonable temporal sequence from administration of the study medication; that follows a known or expected response pattern to the suspected study medication; that is confirmed by stopping or reducing the dosage of the study medication; and that could not be reasonably explained by the known characteristics of the subject's clinical state.
Possible	A reaction that follows a reasonable temporal sequence from administration of the study medication; that follows a known or expected response pattern to the suspected study medication; but that could readily be produced by a number of other factors.
Unlikely	A reaction that does not follow a reasonable temporal sequence from administration of the study medication; that does not follow a known or suspected response pattern to the suspected study medication; and that could reasonably be explained by known characteristics of the subject's clinical state.
Not Related	Any event that does not meet the above criteria.

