## 7.5 Reporting SAEs

In agreeing to the provisions of this protocol, the investigator accepts all legal responsibilities for immediate reporting of SAEs to the Safety Officer.

The Safety Officer for this trial is:

[name]  
[contact]  
Email: [[contact]](mailto:[contact])  
SAE Email: [[contact]](mailto:[contact]) and [[contact]](mailto:[contact])

All SAEs must be reported to the Safety Officer within 2 working days after the investigator identifies the SAE. SAEs should be entered into the OnCore System within 2 working days of the investigator becoming aware of the event. An initial report by telephone should be followed as soon as possible by completion of the SAE CRF. Any supporting source documentation should be emailed to the assigned contact as soon as possible. At a minimum the following information should be provided at the time of the initial report: patient number and initials, a description of the event, at least one criterion classifying the event as Serious, the name and title of the reporting individual, and information regarding study drug dosing. Additionally, judgment of causality by the investigator must be provided as soon as possible to ensure timely reporting to regulatory authorities by the study Sponsor (e.g., CIOMS forms, FDA MedWatch Form 3500A or other equivalent form). Following the initial report, any additional information obtained by the investigator about the SAE must be reported promptly to the Safety Officer.

The investigator will assess whether the event is causally related to the study medication. The study designated physician ([name] or designee) will consider the investigator's assessment, however, since [name] holds the IND and is primarily responsible for the overall safety of the participants, his causality assessment will take precedence over that of the site investigator. The study designated physician will determine if a *suspected, unexpected serious adverse reaction* (SUSAR) in accordance with FDA regulations, 312.32 (c)(1)(i) meets the criteria as being reportable as a 7-day or a 15-day safety report and will submit reports as required to FDA.

Upon becoming aware of an SAE during the conduct of the study, the study designated physician shall inform Intercept of the SAE within the time frames and using the format defined in the table below. Follow-up information shall be shared using the same time frames and

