formats. Additionally, approximately every six months, the study designated physician shall provide Intercept with a list of all SAEs that were received during the previous six months.

Type of SAE:	Format	Time Frame
All SUSARs	MedWatch or CIOMS, with narrative	≤ 5 Calendar Days
SAEs (not meeting criteria for SUSAR)	Aggregate SAE listing with case narratives or MedWatch/CIOMS for each SAE,	Every 6 months

SUSAR and SAE reports are to be sent to Intercept at [[contact]](mailto:[contact]). Intercept may request, in writing, additional information about an SAE at any time, and the study designated physician (or designee) shall respond to the request as efficiently and completely as possible.

The investigator is responsible for submitting information on SUSARs/SAEs received from the Sponsor to her/his local IRB/IEC. The Sponsor will also notify the appropriate regulatory agencies as well as all participating investigators of all SUSARs/SAEs that occur during the trial within the time frames required by each regulatory agency. Documentation of the submissions to IEC/IRBs and health authorities must be retained in the appropriate trial file(s). 7-day or 15-day safety reports should be retained in the appropriate trial files, or with the IB. The Sponsor will follow country specific and local reporting requirements for all SAEs/SUSARs.

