## **8.7 FOLLOW UP OF AEs**

All AEs, including clinically significant laboratory values or physical examination findings relative to pretreatment assessments, must be followed until the AE resolves, is no longer of clinical concern, has stabilized or is otherwise explained, or the patient is lost to follow up.

AEs ongoing at the final visit that are deemed to be 'possibly, probably, or definitely" related or of other clinical significance must be followed for as long as necessary to adequately evaluate the safety of the patient or until the event stabilizes, resolves, or is no longer of clinical concern. If resolved, a resolution date for the AE should be documented on the CRF. The investigator must ensure that follow up includes any supplemental investigations indicated to elucidate the nature and/or causality of the AE. This may include additional laboratory tests or investigations, or consultation with other healthcare professionals, as considered clinically appropriate by the investigator.

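### Table 3 cannot record a new, plausibly timed reaction as Possible or higher, which contradicts the suspected-reaction definition printed just above it

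*Combined protocol and SAP*

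**What the plan says.** All references are to the Combined protocol and SAP. Section 7.3 (Relationship of AEs to Study Medication) has the investigator grade each event against a table. The text cites it as Table 5; it is printed as Table 3. The categories are:

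- **Definite:** reasonable timing or an established drug level, and a reaction "that follows a known or expected response pattern to the suspected drug; and that is confirmed by improvement on stopping or reducing the dosage", with return on re-exposure.
- **Probable:** reasonable timing, the same pattern condition, confirmation when the drug is stopped or reduced, and no reasonable explanation in the subject's clinical state.
- **Possible:** a reaction "that follows a known or expected response pattern to the suspected study medication; but that could readily be produced by a number of other factors", given reasonable timing.
- **Unlikely:** three conditions together, namely no reasonable timing, no recognised pattern, and an explanation in the clinical state.
- **Not Related:** "Any event that does not meet the above criteria".

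The same section calls an event a suspected adverse reaction when there is a reasonable possibility that the drug caused it, and explains the term: "Reasonable possibility' means there is evidence to suggest a causal relationship between the study medication and the AE". That test has no pattern condition, and no sentence says which table categories satisfy it.

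The categories are used in three places. Under section 7.5 (Reporting SAEs) the investigator's causality judgement goes to the study designated physician. Under section 8.7 (Follow up of AEs), events still open at the final visit and deemed, at one of the top three levels, "related or of other clinical significance must be followed for as long as necessary to adequately evaluate the safety of the patient". Under section 9.3 (Safety Analysis, Adverse Events), treatment-emergent events are tabulated by relationship to treatment.

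**The concern.** The three categories that express a link to the drug all require the event to resemble something already recognised for the drug. A reaction seen for the first time cannot meet that condition, however strong the other evidence. If its timing is plausible it cannot be Unlikely either, so it drops to the leftover category.

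This matters here because section 1.1 states that FXR agonists have not been studied in heavy drinkers or in alcoholic liver disease, although section 1.4 mentions an investigation of the same dose in alcoholic cirrhosis. Section 1.4 plans 15 heavy drinkers on OCA, so one misgraded event is 1/15 = 6.7% of the arm. At stake are the causality entry for each such event, the relationship tables built from those entries, and what the study designated physician receives from the site.

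**Working it through.** The plan gives no figure to reproduce. The check treats Table 3 as a decision rule and asks where each kind of event lands.

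**Inputs (all from Table 3).** Seven yes/no conditions: T, reasonable timing; L, drug level established; K, recognised response pattern; D, positive dechallenge; R, positive rechallenge; C, explained by the clinical state; F, readily produced by other factors.

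**Rules as written.**

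- Definite = (T or L) and K and D and R
- Probable = T and K and D and not C
- Possible = T and K and F
- Unlikely = not T and not K and C
- Not Related = anything else

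There are 2^7 = 128 combinations, of which 2^6 = 64 have no recognised pattern (K = no).

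| No recognised pattern | Combinations | Possible or higher | Unlikely | Not Related |
|---|---|---|---|---|
| Timing reasonable | 2^5 = 32 | 0 | 0 | 32 |
| Timing not reasonable | 2^5 = 32 | 0 | 16 | 16 |
| Total | 64 | 0 | 16 | 48 |

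Within the first row, fixing D = R = yes leaves L, C and F free: 2^3 = 8 combinations, all Not Related.

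One simplification was made. Unlikely describes the pattern in slightly different words from the other rows, and the two were treated as one condition. This does not affect the 32 of 32, because those events already fail Unlikely on timing.

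**Second gap.** Take T = yes, K = yes, D = no, F = no. An example is a fatal or irreversible event of a recognised kind, where dechallenge cannot be observed and other factors would not readily produce it. Definite and Probable fail on D, Possible fails on F, and Unlikely fails on T. The result is Not Related.

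**Against the definition in section 7.3.** An event that stops on withdrawal and returns on re-exposure supplies evidence of causation, so it is a suspected adverse reaction under the text. Under the table it is Not Related. It then ranks below an event with implausible timing and an explanation in the clinical state, which is Unlikely.

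**The case against.** A reader might infer more: that the table makes suspected and unexpected mutually exclusive, that no event can ever be a SUSAR, and that notice to the drug manufacturer therefore slips from 5 calendar days to the six-monthly route ("Aggregate SAE listing with case narratives or MedWatch/CIOMS for each SAE"). The documents do not support this.

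- Section 7.5 sends every SAE to the Safety Officer within 2 working days, with no relatedness filter. Section 8.6 does the same for SAEs within 30 days of stopping study medication.
- The study designated physician's causality assessment takes precedence over the site's. That physician decides SUSARs under the FDA regulation, and Table 3 is not named.
- The documents define neither unexpectedness nor a response pattern. An event could fit a known pattern and still be unexpected, for example in severity.
- The slip to six-monthly notice is a worst case. It needs the physician to adopt a Not Related entry unchanged.

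Other points also limit the damage. Section 8.7 first requires all AEs to be followed until they resolve, stabilise or are no longer of concern, and its extended rule also covers events of other clinical significance. All treatment-emergent events are tabulated by arm whatever their relationship, so only the relationship breakdown is distorted. The second gap is narrow because Probable and Possible apply different tests: an event that the clinical state does not explain may still be readily produced by other factors, and is then Possible. The counts above are unweighted combinations of criteria and say nothing about how often such events occur.

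These limits stand, but they do not remove the defect. The override is described only for SAEs, so nothing corrects the grade of a non-serious event. For SAEs it depends on one role reversing what the protocol's only written causality scale produces, and no step is described that would amend the recorded category.

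**Conclusion.** The rule is wrong as written. Read literally, Table 3 cannot grade a new, plausibly timed reaction as Possible or higher, and it sends every such event to Not Related (32 of 32, including all 8 with positive dechallenge and rechallenge). A narrower set of recognised-pattern events without dechallenge information lands there too. Both results contradict the suspected-reaction definition in section 7.3.

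The consequences are wrong recorded causality for serious and non-serious events of these kinds, wrong entries in the tables by relationship, a weakened relatedness trigger for extended follow-up, and a biased investigator input to the SUSAR decision. SUSAR reporting is not closed off.

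The conclusion assumes that investigators apply the table as worded. One who reads the pattern condition loosely would avoid the error, but would then be departing from the stated criteria.

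**What to change.** Reconcile section 7.3, Table 3 and section 7.5 in one amendment:

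1. **Possible:** remove the pattern condition. Define it as reasonable timing plus the evidence test already in section 7.3, whether or not the pattern is known or other factors could contribute, when Probable and Definite are not met.
2. **Probable and Definite:** keep the pattern condition here only, to separate them from Possible.
3. **Not Related:** give it its own definition, namely that the evidence test is not met and Unlikely does not apply. It should no longer be the default.
4. **Mapping:** state that Possible, Probable and Definite count as a reasonable possibility, and that expectedness is judged separately.
5. **Cross-reference:** change the citation of Table 5 to Table 3. Section 7.2 likewise cites Table 3 for severity grades that are printed in Table 2.

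Before adoption, check that each combination of conditions falls in exactly one row, in particular a recognised pattern without reasonable timing.

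The cost is rewording one table and a few sentences. The downside is that somewhat more events will be classed as possibly related.

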### 8.4 SERIOUS ADVERSE EVENTS

#### Definition of a Serious Adverse Event

An adverse event or suspected adverse reaction is considered 'serious' if, in the view of the investigator, it results in any of the following outcomes:

Death;

Is life threatening;  
Results in hospitalization or prolongation of existing hospitalization;  
Results in persistent or significant incapacity or substantial disruption of the ability to conduct normal life functions;  
A congenital anomaly/birth defect;  
An important medical event that may jeopardize the patient or subject and may require medical or surgical intervention to prevent one of the outcomes listed above.

An AE is considered “life-threatening” if, in the view of the investigator, its occurrence places the patient or subject at immediate risk of death. It does not include an AE that, had it occurred in a more severe form, might have caused death.

## 7.5 Reporting SAEs

In agreeing to the provisions of this protocol, the investigator accepts all legal responsibilities for immediate reporting of SAEs to the Safety Officer.

The Safety Officer for this trial is:

[name]  
[contact]  
Email: [[contact]](mailto:[contact])  
SAE Email: [[contact]](mailto:[contact]) and [[contact]](mailto:[contact])

All SAEs must be reported to the Safety Officer within 2 working days after the investigator identifies the SAE. SAEs should be entered into the OnCore System within 2 working days of the investigator becoming aware of the event. An initial report by telephone should be followed as soon as possible by completion of the SAE CRF. Any supporting source documentation should be emailed to the assigned contact as soon as possible. At a minimum the following information should be provided at the time of the initial report: patient number and initials, a description of the event, at least one criterion classifying the event as Serious, the name and title of the reporting individual, and information regarding study drug dosing. Additionally, judgment of causality by the investigator must be provided as soon as possible to ensure timely reporting to regulatory authorities by the study Sponsor (e.g., CIOMS forms, FDA MedWatch Form 3500A or other equivalent form). Following the initial report, any additional information obtained by the investigator about the SAE must be reported promptly to the Safety Officer.

The investigator will assess whether the event is causally related to the study medication. The study designated physician ([name] or designee) will consider the investigator's assessment, however, since [name] holds the IND and is primarily responsible for the overall safety of the participants, his causality assessment will take precedence over that of the site investigator. The study designated physician will determine if a *suspected, unexpected serious adverse reaction* (SUSAR) in accordance with FDA regulations, 312.32 (c)(1)(i) meets the criteria as being reportable as a 7-day or a 15-day safety report and will submit reports as required to FDA.

Upon becoming aware of an SAE during the conduct of the study, the study designated physician shall inform Intercept of the SAE within the time frames and using the format defined in the table below. Follow-up information shall be shared using the same time frames and

formats. Additionally, approximately every six months, the study designated physician shall provide Intercept with a list of all SAEs that were received during the previous six months.

Type of SAE:	Format	Time Frame
All SUSARs	MedWatch or CIOMS, with narrative	≤ 5 Calendar Days
SAEs (not meeting criteria for SUSAR)	Aggregate SAE listing with case narratives or MedWatch/CIOMS for each SAE,	Every 6 months

SUSAR and SAE reports are to be sent to Intercept at [[contact]](mailto:[contact]). Intercept may request, in writing, additional information about an SAE at any time, and the study designated physician (or designee) shall respond to the request as efficiently and completely as possible.

The investigator is responsible for submitting information on SUSARs/SAEs received from the Sponsor to her/his local IRB/IEC. The Sponsor will also notify the appropriate regulatory agencies as well as all participating investigators of all SUSARs/SAEs that occur during the trial within the time frames required by each regulatory agency. Documentation of the submissions to IEC/IRBs and health authorities must be retained in the appropriate trial file(s). 7-day or 15-day safety reports should be retained in the appropriate trial files, or with the IB. The Sponsor will follow country specific and local reporting requirements for all SAEs/SUSARs.

#### *Additional Principal Investigator Responsibilities for SAEs*

The safety data recorded in the CRF represent the official record of all AEs and SAEs reported in the trial. The investigator should comply with requests by the Safety Officer to record the SAE on the patient's AE CRF and, if necessary, provide a copy of this CRF to the sponsor. Other supporting documents such as radiology reports, hospital discharge summaries and autopsy reports should also be provided, when appropriate. Additionally, upon request by the Safety Officer, the investigator should provide input into the SAE narrative and provide timely information to ensure prompt follow up and closure of the SAE report.

The investigator and supporting personnel responsible for patient care should discuss with the Safety Officer any need for supplemental investigations of SAE(s).

#### **8.6 NOTIFICATION OF POST-TRIAL SAEs**

If the investigator becomes aware of an SAE that may be attributable to the study medication at any time after the end of the trial, the study designated physician should be notified within 2 working days.

All SAEs that occur within 30 days following the cessation of study medication, whether or not they are related to the study medication, must be reported to the

study designated physician within 2 working days by following the instructions provided in Section 7.5.

## **8.7 FOLLOW UP OF AEs**

All AEs, including clinically significant laboratory values or physical examination findings relative to pretreatment assessments, must be followed until the AE resolves, is no longer of clinical concern, has stabilized or is otherwise explained, or the patient is lost to follow up.

AEs ongoing at the final visit that are deemed to be 'possibly, probably, or definitely" related or of other clinical significance must be followed for as long as necessary to adequately evaluate the safety of the patient or until the event stabilizes, resolves, or is no longer of clinical concern. If resolved, a resolution date for the AE should be documented on the CRF. The investigator must ensure that follow up includes any supplemental investigations indicated to elucidate the nature and/or causality of the AE. This may include additional laboratory tests or investigations, or consultation with other healthcare professionals, as considered clinically appropriate by the investigator.

## **8. DRUG INTERACTION**

OCA 10 mg has shown potential weak inhibition on CYP1A2, BCRP, OATP1B1, and OATP1B3 (Rosuvastatin), and CYP2C19 (Omeprazole). The list of the medications (if any) of subjects will be reviewed by the PI before the study. Additionally, considering warfarin, metabolized by CYP2C9, is a narrow therapeutic drug, we will exclude subjects who are on warfarin from the study.

## **9. STATISTICAL METHODS**

### **9.1 Cross-sectional Component:**

**Primary end point:** The mean(SD) will be used to summarize the baseline the C4 and FGF19 level at baseline. The primary analysis is to compare the C4 and FGF19 level at baseline between the 15 health control and 30 heavy drinker using independent two-sample t-tests. The distribution assumption of C4 and FGF19 will be examined for the distribution assumption. If there is an assumption violation, appropriate transformation will be used to correct the assumption violation. We will also perform analysis of covariance (ANCOVA) analysis with C4(FGF19) at baseline as the outcome variable, group(health control vs. heavy drinker) as the main predictor adjusting for patients' characteristics.

**The secondary endpoints** (a) fasting serum bile salt levels, oxidative stress and CYP2E1 activity; (c) gut permeability, bacterial translocation, and intestinal inflammation; and (d) activation of innate immunity at baseline will also be compared using two-sample t-test and the ANCOVA models in a similar way to C4 and FGF19.

**Power analysis:** For the cross-sectional study, there are 15 health and 30 heavy drinker. We use two-sample t-test for comparison of the primary endpoint C4 and FGF19. With these sample size, we will have 83% power to detect any difference in C4(or FGF19) of effect size equal to or greater than 0.95(mean/SD) with a 5% Type I error rate.

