### **9.2 Longitudinal component:**

**Primary endpoint:** In the intervention phase, the main goal is to see whether OCA will alternate or reverse the C4(FGF19). So the main analysis to use two-sample t-test to compare the change of C4(FGF19) from baseline to 4 weeks between the randomized treated and placebo arm. The secondary analysis for the primary end points is to compare the C4 (FEF19) level at 4 week using two-sample t-tests to see whether the C4 level of the treated group has recover to the normal control level after 4 weeks treatment.

**The secondary endpoint** will be compared using two-sample t-tests in a similar way to the primary endpoints.

**Power analysis:** For the intervention study, there are 15 subjects in each group. We use two-sample t-test for comparison of the change of C4 and FGF19. With these sample size, we will have 82% power to detect any difference in change of C4(or FGF19) of effect size equal to or greater than 1.11(mean/SD) with a 5% Type I error rate.

**9.3 Safety Analysis:** Descriptive statistics will be used to summarize the AEs if occur.

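### The analysis scale for C4 and FGF19 is left open at baseline and not stated for the randomised comparison; naming the log scale in advance, with baseline-adjusted ANCOVA in 9.2, is a cheap improvement

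*Combined protocol and SAP*

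**What the plan says.** **Section 9.1 (cross-sectional, 15 controls v 30 heavy drinkers).** The primary analysis is a two-sample t-test on baseline C4 and FGF19. On distribution it says "The distribution assumption of C4 and FGF19 will be examined for the distribution assumption", and then that, on a violation, "appropriate transformation will be used to correct the assumption violation". It names no test, threshold, transformation or timing. An ANCOVA adjusting for patient characteristics is also planned. The secondary markers follow the same approach.

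**Section 9.2 (randomised, OCA v placebo).** The main analysis is a "two-sample t-test to compare the change of C4(FGF19) from baseline to 4 weeks between the randomized treated and placebo arm". No distribution check, transformation or baseline adjustment is mentioned. A further comparison of week-4 levels, meant to show whether treated subjects have returned to the control level, also has no stated scale. The secondary endpoint "will be compared using two-sample t-tests in a similar way to the primary endpoints".

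**Power.** Section 9.2 states that "For the intervention study, there are 15 subjects in each group" and claims "82% power to detect any difference in change of C4(or FGF19) of effect size equal to or greater than 1.11(mean/SD"). Section 9.1 claims 83% power at 0.95 SD. Neither section gives an SD, CV, correlation or distribution. Section 5.2 leaves the calculated definition of baseline to a SAP, but the documents contain no further rule on scale.

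**The concern.** The objectives link two quantities: the gap between drinkers and controls at baseline, and the change that OCA produces. As written, the first may be analysed on a transformed scale and the second on the original scale. The two estimates could not then be set against each other directly.

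The choice also affects efficiency. C4 and FGF19 are positive concentrations, and for such markers an effect may be closer to proportional than additive. If so, a t-test on untransformed change can be an inefficient use of 15 subjects per arm. How inefficient depends on the direction of the effect, and the two primary endpoints are expected to move in opposite directions: Section 1.4 reports that C4 fell and FGF19 rose on OCA.

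**Working it through.** **1. Reproduce the plan's power.** Equal-variance two-sample t-test, two-sided 5%, with noncentrality d × √(n1·n2/(n1+n2)).
- Section 9.2: 1.11 × √(225/30) = 1.11 × 2.739 = 3.04 on 28 df, giving 83.5% (stated 82%).
- Section 9.1: 0.95 × √(450/45) = 0.95 × 3.162 = 3.00 on 43 df, giving 83.6% (stated 83%).

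Both agree within two points. A one-sided test gives about 91% and does not reproduce them.

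**2. Assume a model, since the documents give none.** Baseline and week-4 values are lognormal with log-SD s and log-scale correlation r. The SD of log change is s√(2(1−r)), and the effect is set at 1.11 times that. Example: s = 0.5, r = 0.5 gives an SD of 0.5 and an effect of 0.555, a ratio of exp(−0.555) = 0.57 for a fall or exp(0.555) = 1.74 for a rise. CV = √(exp(s²)−1).

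**3. Simulated power of the t-test, 15 per arm, 20,000 trials per setting, r from 0.3 to 0.8.**

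| log-SD (CV) | Log change | Untransformed change, fall (C4) | Loss, points | Untransformed change, rise (FGF19) | Loss, points |
|---|---|---|---|---|---|
| 0.3 (31%) | 83-84% | 73-75% | 9 to 11 | 84-87% | −4 to 0 |
| 0.5 (53%) | 83-84% | 61-66% | 18 to 23 | 80-86% | −3 to 4 |
| 0.7 (80%) | 83-84% | 50-55% | 29 to 34 | 73-83% | 0 to 11 |

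Repeat runs differ by about one point; one gave 76% as the upper end of the first row for a fall.

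**4. Put the effect where 9.2 puts it.** Section 9.2 defines 1.11 as a difference in change divided by its SD. At r = 0.5, the falls in step 3 amount to only 0.96, 0.83 and 0.69 SD of untransformed change, which is why power drops. If the same skewed data are given a difference of 1.11 SD in untransformed change, the t-test has about 85%, 86% and 88% power for a fall and 85%, 88% and 93% for a rise. The stated 82% is then met.

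**5. The alternative: ANCOVA of log(week 4) on arm and log(baseline).** The residual SD is s√(1−r²), so the standardised effect becomes 1.11 × √(2(1−r))/√(1−r²) = 1.11 × √(2/(1+r)). That is 1.38 at r = 0.3, 1.28 at r = 0.5 and 1.17 at r = 0.8. It depends on neither s nor direction. Simulated power is 85-95% across the lognormal settings. The gain over log change comes from the baseline adjustment.

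**6. If the data are in fact normal with an additive effect (CV 15-30%, r = 0.5).** Untransformed change has 83-84% power and the log ANCOVA 87-91%. The unadjusted log ratio loses 4 to 13 points for a rise. At CV 30% a normal model puts some week-4 values near zero after a fall. The log ANCOVA result then depends on how those values are handled, and it can drop to about the 83% of untransformed change.

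**The case against.** The strongest reply is that 9.2 defines its effect on the change itself, and on that definition its power statement is right (step 4). That stands. A reader might infer from the C4 column that the stated 82% is not reached. The documents do not support this: the shortfall appears only when 1.11 SD is moved to the log scale, and they give no SD or distribution that would require the move. Section 1.4 even quotes C4 effects as absolute changes in ng/ml.

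Three other inferences also go too far.
- **A general loss of 20 to 30 points.** This holds for a fall at log-SD of about 0.5 to 0.7. For a rise over log-SD 0.3 to 0.7 the result ranges from a small gain to an 11-point loss.
- **Inflated type I error from choosing the scale late.** A rule that transforms only when a violation is found keeps the error at about 5.0-5.6% in simulation. About 5.9-7.1% arises only if the smallest p-value among raw, log and square root is picked, which 9.1 does not say.
- **A distribution check too weak to work.** At log-SD 0.5 a Shapiro-Wilk test finds skewness in about 40% of samples of 15. But the check in 9.1 covers 45 subjects, where detection is about 86%, and 9.1 does not name that test.

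It is also fair to say that 9.2 is silent rather than prescriptive. Untransformed change is the plain reading, not a stated rule. What remains is that the scale is unnamed in one section and unaddressed in the other.

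**Conclusion.** The point holds in a limited form. The scale is not fixed in advance in 9.1 and not mentioned in 9.2, so the two components may end up on different scales. The power cost is conditional on lognormal data and a proportional effect of 1.11 SD of log change. Over log-SD 0.3 to 0.7 it is about 9 to 34 points for C4 and about −4 to 11 points for FGF19. There is no shortfall against the stated 82% if untransformed change differs by 1.11 SD. The case for changing the plan rests on consistency between the components, and on a baseline-adjusted log analysis doing better than the t-test on untransformed change in nearly every setting examined, with the near-zero caveat in step 6. This is a cheap improvement, not an error that invalidates the plan.

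**What to change.** - In 9.1 and 9.2, name the log scale for C4 and FGF19 before the data are examined, in place of the open-ended transformation rule.
- In 9.2, make the primary analysis of the randomised arms an ANCOVA of log(week 4) on arm and log(baseline), rather than a t-test on untransformed change or on the unadjusted log ratio.
- Report geometric-mean ratios with 95% CI in both components, so that the baseline gap and the OCA effect can be compared.
- Optionally, add a rank-based test as a sensitivity analysis.

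The cost is wording in two sections. No extra subjects, visits or assays are needed, because baseline and week-4 values are already collected. The downside is that effects are reported as ratios rather than in assay units.
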